1.0 Title

"Ear Plugs and Eye Mask To Improve Night Sleep Duration In Nulliparas. A Randomised Control Trial"

2.0 Introduction

75% of pregnant women experience some form of sleep disruption during pregnancy. [1] The rate of sleep disturbances also changes across trimesters, ranging from 13% in the first trimester, 19% in the second, and 66% in the third. Lack of sleep in third trimester has detrimental effect on pregnancy outcomes [2].

Women who reported less than 6 hours of sleep per night during the last month of pregnancy had a significantly longer mean duration of Labour (29 hours vs. ≥20 hours) and a higher rate of caesarean births (< 6 hours: 37%; 6-6.9 hours: 34%; 7+ hours: 11%, p-value < 0.05) [3]. Women who slept less than 7 hours at night are at increased risk of developing gestational diabetes, gestational hypertension and preterm birth [4][5][6].

Hypnotic drugs can have adverse effect on the mother and fetus, and such drugs safe for women to take during pregnancy are limited [7][8]. Psychological and behavioural therapies, acupuncture and herbal treatments have shown some promising result in treating insomnia during pregnancy [9].

Sensory deprivation methods such as eye masks and ear plugs have been shown to increase the sleep duration by 41-59% among in ICU patients [10][11][12].

We hypothesized that eye masks and ear plugs will increase night sleep duration among nulliparas in their third trimester who reported sleep duration less than 6 hours . (< 6hours represents lower half of reported night sleep duration in our center) [13].

We plan to perform a powered study on impact of eye mask and ear plugs in late third trimester at 34 to 36 weeks nulliparas utilising the actigraph device to objectively quantify night sleep duration.

3.0 Objectives:

Primary Objectives

1. To study the Effectiveness of ear plugs and eye mask in improving night sleep duration among nulliparas at 34-36 weeks gestation.

Secondary Objectives:

- 1. To study the effectiveness of eye masks and ear plugs in improving Wake after sleep onset (WASO) and Sleep efficiency (SE)
- 2. To Study the effect of eye masks and ear plugs in improving labour outcomes among pregnant mothers with sleep disturbances.

a. Maternal:

- Mode of delivery
- Indication for Caesarean delivery
- Need for Labor induction: Prostaglandin or Amiotomy.
- Peridelivery blood loss.
- Epidural requirement

b. Fetal

- Birth weight.
- Cord ph and base excess
- Apgar score at 5 minute.
- Neonatal admission and indication
- 3. Subjects' sleep satisfaction with sleep aid based on likert scale.

4.0 Research Hypothesis

Ear plugs and eye masks will increase night sleep duration among nulliparas with short self-reported night sleep duration in their late third trimester.

5.0 Methodology

5.1 Study type and design

This is a randomised control trial.

5.2 Study Population

Nulliparas who attend Antenatal Clinic at University Malaya Medical Center

5.3 Inclusion criteria:

- Nulliparous
- 34 36 weeks of gestation.
- Self-reported sleep of less than 6 hours.
- Singleton pregnancy

5.4 Exclusion criteria:

- Patients with known pre-existing sleep disorders: Chronic insomnia, Sleep apnea.
- Patients with known pre-existing psychiatric disorders eg: depression, schizophrenia etc.
- Patients with underlying medical disorders: SLE, Thyroid disorders, Epilepsy, Heart diseases etc.
- Night shift workers
- Active smoker
- Current alcoholic consumption
- Obesity > class II (BMI > 35)
- Intrauterine Death
- Care taker of other family members.
- Gross fetal anomaly

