5.7 Study Design

This is a randomised control trial. Nulliparas, who are at 34 – 36 weeks who attend Antenatal clinic in UMMC and reported night sleep duration of 5 hours or less on average in the last 1 month will be informed regarding this study. Patient information sheet will be provided for those who fulfilled initial eligible criteria. Those who agreed to participate will be asked to provide written consent, and agree to participate in this study, will be recruited.

They will be provided with Actisleep and taught on methods to use it. They need to wear it when they sleep at night 7 consecutive nights. Time in bed (TIB) and Time out of bed (TOB) need to be recorded every night.

After 7 days, they need return to Antenatal clinic, their sleep data will be retrieved from the Actisleep device. They can proceed with the study only if 3 days of usable readings are recorded. Randomisation with the intention to treat with a specific intervention or placebosham method will follow.

They will be randomised into 2 groups. interventional group or Placebo using sham method, based on a randomisation sequence generated using random.org in a random block of 4 or 8 sequence, generated by investigator not involved in the recruitment process. Randomisation is by the opening of sealed opaque and numbered envelope with lowest available envelope assigned in strict order.

A. Interventional Group: Eye masks and ear plugs.

Subjects are provided with eye masks and ear plugs to wear when they go to bed at night, for 7 consecutive nights. Time in bed(TIB) and time out of bed (TOB) needs to be recorded every night. They may remove the eye masks and ear plugs temporarily if they wake up from sleep at night.

At the end of 7 days, subjects will return to Antenatal clinic and have the Actisleep analysed and returned to the investigator.

Placebo Group

Subjects are provided with an elasticated headband to wear when they go to bed at night, for 7 consecutive nights. Headband shall be placed on their forehead loosely. Time in bed(TIB) and time out of bed (TOB) needs to be recorded every night.

[figure not shown]
At the end of 7 days, subjects will return to Antenatal clinic and have the Actisleep analysed and returned to the investigator.

Patients labor and neonatal outcomes will be analysed after they delivered.

At the end of the study, subject's satisfaction on their sleep quality will be assessed based on likert satisfaction scale.

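### Women with a prelabour caesarean already planned are eligible, which modestly dilutes four labour-related secondary outcomes; recording planned status before allocation would cheaply repair this.

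*Protocol*

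**What the plan says.** Section 5.3 has four inclusion criteria: nulliparity, 34 to 36 weeks, short self-reported sleep and "Singleton pregnancy". Section 5.4 has ten exclusions. The nearest to the point is "Patients with underlying medical disorders: SLE, Thyroid disorders, Epilepsy, Heart diseases etc", which names maternal medical disease and no obstetric reason for avoiding labour. The last items include "Care taker of other family members", intrauterine death and gross fetal anomaly. Planned caesarean is not mentioned.

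Secondary objective 2 in Section 3.0 reads "To Study the effect of eye masks and ear plugs in improving labour outcomes among pregnant mothers with sleep disturbances". Its maternal list includes "Mode of delivery", "Indication for Caesarean delivery", "Need for Labor induction: Prostaglandin or Amiotomy" and epidural requirement, as well as peridelivery blood loss. Section 5.7 adds "Patients labor and neonatal outcomes will be analysed after they delivered". Section 5.9.2 names general tests only.

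The data collection form records induction, amniotomy, analgesia and a three-way mode of delivery (spontaneous, instrumental, caesarean). It has three free-text lines for antenatal problems and no field for planned versus intrapartum caesarean.

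**The concern.** A nullipara with, for example, a low-lying placenta and a booked caesarean meets every criterion. Whatever the sleep aid does for her, she is likely to be recorded as a caesarean, as not induced, and as having no epidural for labour. The objective is about improving labour outcomes, yet part of the eligible population is not expected to labour.

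Such women add the same event to both arms in expectation, so any true effect in the others is diluted. The Introduction uses caesarean rates as part of its case for studying sleep, so mode of delivery matters to the rationale. If planned status is not captured before allocation, a later analysis plan would have to reconstruct it from free text or from the caesarean indication, and neither reliably shows what was planned at randomisation.

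**Working it through.** **Eligibility against objective.** Four inclusion and ten exclusion criteria were read against the four outcomes. None requires planned labour and none removes a planned caesarean. No section restricts the four outcomes to women planned for labour.

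**No figure to reproduce.** The protocol gives neither a planned-caesarean share nor a target for any labour outcome. What follows is an illustration.

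**Inputs.**
- Caesarean rates of 37% (under 6 hours of sleep) and 11% (7 hours or more), from the Introduction. The protocol does not set this contrast as a trial target.
- 25 women per arm, from the 50 planned in Section 5.9.1.
- Two-sided alpha of 0.05 (assumed for this illustration).
- Booked share q, equal in both arms: 2%, 5% and 10% (assumptions).

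**Dilution.** With a share q booked, each arm's rate becomes q + (1 − q)p, so the difference shrinks to (1 − q) × 26 points.
- q = 2%: 0.02 + 0.98 × 0.37 = 38.26%, and 0.02 + 0.98 × 0.11 = 12.78%; difference 25.48 points.
- q = 5%: 40.15% v 15.45%; difference 24.70 points.
- q = 10%: 43.30% v 19.90%; difference 23.40 points.

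**Power.** Power = Φ[(d − 1.96 × SE0) / SE1], where SE0 = √(2 p̄(1 − p̄)/n) and SE1 = √([p1(1 − p1) + p2(1 − p2)]/n).
- q = 0: p̄ = 0.24, SE0 = 0.1208, SE1 = 0.1151; Φ[(0.26 − 0.2368)/0.1151] = 58%.
- q = 5%: p̄ = 0.278, SE0 = 0.1267, SE1 = 0.1218; Φ[(0.247 − 0.2484)/0.1218] = 50%.

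For the restricted analysis the rates stay at 37% and 11%, and n falls to 25(1 − q).

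| Booked share (assumed) | Power, all randomised | Women per arm if restricted | Power, restricted |
|---|---|---|---|
| 0% | 58% | 25 | 58% |
| 2% | 54% | 24.5 | 57% |
| 5% | 50% | 23.75 | 56% |
| 10% | 43% | 22.5 | 53% |

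Restriction recovers about 3, 6 and 11 percentage points of power.

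**Chance imbalance.** The standard error of the between-arm difference, with both arms at one rate p, is √(2p(1 − p)/n). At p = 37% and n = 25 it is 13.7 points with no one booked. At q = 10%, p = 43.3% and it is 14.0 points. Booked women add almost nothing to the noise already present.

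**The case against.** The best case against has four parts.

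- **An analysis plan could define the labour population.** That is fair for the definition, and such a plan may exist. It does not cover the baseline record: eligibility and what is recorded before allocation belong to the protocol and its form, and a status not recorded then cannot be reliably recovered later. This limited part of the point stands.
- **Some of the information is already collected.** Caesarean indication is a listed outcome, and the antenatal-problem lines may show the reason for a booking. This narrows the gap. Free text still does not state what was planned at randomisation.
- **The share may be small.** Nulliparity and singleton pregnancy already rule out repeat caesareans and multiple pregnancies. At 2% booked, the loss of power is slight.
- **These outcomes are weak anyway.** Only sleep duration is powered, and even 37% v 11% has 58% power with no one booked. This stands, and it limits the weight of the point.

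A reader might also infer more than the text supports:

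- *That the comparison is biased, or that a chance imbalance could create a false finding.* Randomisation balances these women in expectation, and an imbalance of one or two is ordinary sampling noise, as the standard errors show.
- *That Section 5.7 commits to analysing all women.* Its sentence gives the timing and is silent on the population.
- *That blood loss is invalid too.* The outcome is peridelivery blood loss, which can be measured validly at caesarean, as can the neonatal outcomes.
- *That the four outcomes are wholly fixed.* A booking can change, and labour can start first.

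**Conclusion.** The point holds as a cheap improvement to one secondary objective. Eligibility admits women for whom mode of delivery, caesarean indication, induction and epidural requirement are largely settled before allocation, and the form does not identify them. The consequence is modest dilution: in the illustration, power for mode of delivery is 54%, 50% and 43% with 2%, 5% and 10% booked, against 57%, 56% and 53% with restriction. These figures rest on assumed booked shares, on the cited 37% v 11% holding in the other women, and on all 25 per arm contributing. They show scale and do not predict this trial. The primary sleep outcome, its sample size and the validity of the randomised comparison are unaffected.

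**What to change.** Add one tick box to the data collection form, completed before the envelope is opened: prelabour caesarean planned, yes or no. Add one sentence to Section 5.7 saying that mode of delivery, caesarean indication, induction and epidural requirement are analysed in randomised women with no caesarean planned at randomisation, with the all-randomised result shown alongside. Keep all women for the sleep outcomes, peridelivery blood loss and neonatal outcomes.

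Because the status is set before allocation, the restriction introduces no selection bias; restricting afterwards to women who actually laboured could. The cost is slightly fewer women in the four tables: at an assumed 10% booked, 50 × 0.10 = 5 of the 50. Eligibility and recruitment need not change.

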5.5 Study Period

Data collection is 6 months

Study period 12 months

5.6 Study Evaluation

Actigraphy – Actisleep Device

Polysomnography(PSG) is considered the "gold standard," for sleep study, however, they are expensive, often requiring participants to sleep in a laboratory, limiting their usability [14]. Wrist actigraphy is an acceptable alternative objective method to assess sleep duration [15]. When compared to PSG, wrist actigraphy demonstrates a correlation (r) of over 0.8 for sleep duration, including studies of pregnant women [16]. Actigraphy is often preferable for objectively measuring sleep duration because it is unobtrusive similar to a wristwatch, ambulatory, and can record for multiple days and nights at a much lower cost than PSG.

The ActiSleep is recommended to be worn at the wrist for general sleep assessment. However, in certain circumstances, waist placement or ankle placement may be allowed. The ActiSleep monitor does not need to make contact with the skin. It must simply fit snuggly against the body and not be allowed to wobble around. It can be worn exclusively during sleep episodes.

The patient should keep a record of Time in Bed (TIB) and Time out of bed (TOB) for each measured sleep episode. The patient should be instructed to return this completed sleep log with the ActiSleep monitor. The TIB and TOB are required for the analysis of sleep data.

Sleep Data

Manufacturer: Actigraph, [name]

Model number: GT3X+

Software version: ActiLife version 6

Data: total sleep time (TST), sleep efficiency (SE), sleep onset latency (SOL) and wake after

sleep onset (WASO)

5.7 Study Design

This is a randomised control trial. Nulliparas, who are at 34 – 36 weeks who attend Antenatal clinic in UMMC and reported night sleep duration of 5 hours or less on average in the last 1 month will be informed regarding this study. Patient information sheet will be provided for those who fulfilled initial eligible criteria. Those who agreed to participate will be asked to provide written consent, and agree to participate in this study, will be recruited.

They will be provided with Actisleep and taught on methods to use it. They need to wear it when they sleep at night 7 consecutive nights. Time in bed (TIB) and Time out of bed (TOB) need to be recorded every night.

After 7 days, they need return to Antenatal clinic, their sleep data will be retrieved from the Actisleep device. They can proceed with the study only if 3 days of usable readings are recorded. Randomisation with the intention to treat with a specific intervention or placebosham method will follow.

They will be randomised into 2 groups. interventional group or Placebo using sham method, based on a randomisation sequence generated using random.org in a random block of 4 or 8 sequence, generated by investigator not involved in the recruitment process. Randomisation is by the opening of sealed opaque and numbered envelope with lowest available envelope assigned in strict order.

A. Interventional Group: Eye masks and ear plugs.

Subjects are provided with eye masks and ear plugs to wear when they go to bed at night, for 7 consecutive nights. Time in bed(TIB) and time out of bed (TOB) needs to be recorded every night. They may remove the eye masks and ear plugs temporarily if they wake up from sleep at night.

At the end of 7 days, subjects will return to Antenatal clinic and have the Actisleep analysed and returned to the investigator.

Placebo Group

Subjects are provided with an elasticated headband to wear when they go to bed at night, for 7 consecutive nights. Headband shall be placed on their forehead loosely. Time in bed(TIB) and time out of bed (TOB) needs to be recorded every night.

[figure not shown]
At the end of 7 days, subjects will return to Antenatal clinic and have the Actisleep analysed and returned to the investigator.

Patients labor and neonatal outcomes will be analysed after they delivered.

At the end of the study, subject's satisfaction on their sleep quality will be assessed based on likert satisfaction scale.

5.8 Schematic Diagram of study design

Eligibility

5.9 Statistical Analysis Plan

5.9.1 Sample size calculation

Our primary outcome is the increase of night sleep duration among nulliparas who reported short sleep duration of 5 hours or less.

There were no previous similar study regarding the use of Eye masks and Ear plugs in improving sleep in pregnancy.

Studies on ICU patients which increase of Total Sleep Time of 41 - 59% [10-12]. We postulate modest improvement of night sleep duration of 1 hour, which is 20% of 5 hours.

Assuming a normal distribution, standard deviation of 1.1hour, obtained from Lee and Gay[3]. 20 patients will be required in each arm to achieve statistical power of 90% (β 0.1) with alpha (α) of 0.05, 1 to 1 ratio across trial arms.

Factoring in dropout rate of 20%, we plan recruit 50 subjects for a suitably powered study

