5.9.2 STATISTICAL ANALYSIS

Data will be entered into SPSS statistical software. Normally distributed continuous data will be analysed with Student's t test. Chi square test will be used for categorical or nominal data and Mann-Whitney U test will be used on non-normally distributed continuous or ordinal data. P < 0.05 is taken as level of significance.

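### Twenty women per arm do not give the stated 90% power: on the protocol's inputs the power is about 80% for a two-sided 5% test and 88–89% for a one-sided one, and the protocol does not say which applies

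*Protocol*

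**What the plan says.** All inputs to the sample size stand in Protocol section 5.9.1.

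- **Effect:** "We postulate modest improvement of night sleep duration of 1 hour, which is 20% of 5 hours".
- **Spread:** "Assuming a normal distribution, standard deviation of 1.1hour", attributed to a published study of sleep in late pregnancy.
- **Size, power and error rate:** "20 patients will be required in each arm to achieve statistical power of 90% (β 0.1) with alpha (α) of 0.05", with a "1 to 1 ratio across trial arms".
- **Recruitment:** "Factoring in dropout rate of 20%, we plan recruit 50 subjects for a suitably powered study".

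Section 5.9.2 names Student's t test for normally distributed continuous data and sets one threshold for all tests: "P < 0.05 is taken as level of significance". Neither section says whether alpha is one-sided or two-sided. The research hypothesis in section 4.0 is directional: it expects sleep duration to increase.

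**The concern.** Difference, standard deviation, alpha, allocation ratio and test are all given, so the power at 20 per arm can be recomputed once sidedness is fixed. Under the usual two-sided convention the result is 80%, not 90%.

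This is the only power statement in the protocol, and it is the basis on which 50 women are called enough. If the test is two-sided, the chance of missing a true 1-hour benefit is about one in five rather than the stated one in ten. If it is one-sided, the shortfall is small, but the reader has not been told that a one-sided 5% test is planned. Either way, the stated power and the stated number do not agree.

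**Working it through.** **Inputs.** From section 5.9.1: difference δ = 1 h, standard deviation σ = 1.1 h, α = 0.05, 1:1 allocation, n = 20 per arm, stated power 0.90. From section 5.9.2: Student's t test, taken here as comparing two independent arms. Sidedness is not given, so both cases are worked.

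**Step 1. Number per arm, normal approximation.**

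n = 2(z_α + z_power)² σ²/δ², with 2σ²/δ² = 2 × 1.21 = 2.42

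- Two-sided, 90%: (1.960 + 1.2816)² × 2.42 = 10.51 × 2.42 = 25.4, so 26 per arm.
- One-sided, 90%: (1.645 + 1.2816)² × 2.42 = 8.56 × 2.42 = 20.7, so 21 per arm.
- Two-sided, 80%: (1.960 + 0.8416)² × 2.42 = 7.85 × 2.42 = 19.0, so 19 per arm.

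No 90% calculation returns 20. The nearest is the one-sided value of 20.7, and reaching 20 from it means rounding down.

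**Step 2. Number per arm, t test (noncentral t).**

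- Two-sided, 90%: 26.4, so 27 per arm.
- One-sided, 90%: 21.4, so 22 per arm.
- Two-sided, 80%: 20.00.

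**Step 3. Power at 20 per arm.**

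Noncentrality = δ / (σ√(2/n)) = 1 / (1.1 × √0.1) = 1 / 0.3479 = 2.875, with 38 degrees of freedom.

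- Normal approximation, two-sided: Φ(2.875 − 1.960) = Φ(0.915) = 0.820.
- Normal approximation, one-sided: Φ(2.875 − 1.645) = Φ(1.230) = 0.891.
- The t-test values come from the noncentral t distribution with critical values 2.024 (two-sided) and 1.686 (one-sided).

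| Test at 5% | Power at 20/arm (t) | Power at 20/arm (normal) | n/arm for 90% (t) | n/arm for 90% (normal) |
|---|---|---|---|---|
| Stated in 5.9.1 | 90% | 90% | 20 | 20 |
| Two-sided | 80.0% | 82.0% | 27 | 26 |
| One-sided | 88.1% | 89.1% | 22 | 21 |

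**Step 4. Dropout.** 2 × 20 = 40, and 40/(1 − 0.20) = 50. This step is correct.

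**Step 5. If nobody drops out (25 per arm).** Noncentrality = 1 / (1.1 × √0.08) = 3.214. Two-sided power is 88.3% (t) or 89.5% (normal), still under 90%. One-sided power is 93.6% (t), which exceeds it.

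**Step 6. What would make 20 per arm right.** With a two-sided t test, 90% power at 20 per arm needs a difference of 1.16 h instead of 1 h, or a standard deviation of 0.95 h instead of 1.1 h.

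**The case against.** The strongest reply is that the 80% figure depends on an input the protocol does not supply. Section 5.9.1 gives an alpha of 0.05 and section 5.9.2 a P threshold, both without sidedness. The hypothesis is directional and the primary outcome is framed as an increase. On a one-sided reading the stated figure is missed by only one or two women per arm and one or two points of power, and beta is 0.11–0.12.

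Much of this stands. A reader might infer that the power is simply 80% and the false-negative risk simply doubled. The documents do not support that without a condition: it holds for a two-sided test, and two-sidedness is an assumption here. The assumption is reasonable, because one threshold serves the t, chi-square and Mann-Whitney tests alike, no one-sided test is mentioned anywhere, and a directional research hypothesis is not a test specification. But it remains an assumption. What does not stand is that the one-sided reading clears the statement, since 20 per arm still falls short of 90%.

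Three further inferences go too far.

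- That 90% is out of reach even with no dropout. This is true two-sided (88%) but not one-sided (93.6%).
- That the authors computed 80% power and mislabelled it. Twenty matches the two-sided t-test answer for 80%, but it also lies close to the one-sided answer for 90%, and the protocol does not show the calculation.
- That a null result would be over-read as proof of no effect. The protocol has no rule for interpreting a null result, so this is conjecture.

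It could also be said that the baseline week allows an adjusted analysis with more power. At an assumed baseline-to-follow-up correlation of 0.5, adjustment would give 89.9% at 20 per arm in a two-sided test. The protocol plans no such adjustment in section 5.9 and states no correlation, so this cannot be the basis of its figure.

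**Conclusion.** The point holds. With a 1 h difference, a standard deviation of 1.1 h and alpha 0.05, 20 women per arm do not give 90% power in either a two-sided or a one-sided two-sample test.

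The size of the error depends on sidedness. On the two-sided convention it is about ten percentage points by the t test (eight by the normal approximation), and the study is six or seven evaluable women per arm short of its stated target. On a one-sided 5% test it is one to two points, or one to two women per arm.

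The conclusion takes the protocol's difference and standard deviation at face value and applies the standard deviation directly to the quantity compared between arms. The protocol does not say whether 1.1 h refers to sleep duration or to its change.

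**What to change.** State in sections 5.9.1 and 5.9.2 that the test is two-sided, and restate the power in 5.9.1 along these lines: *20 evaluable women per arm (50 recruited, allowing for 20% dropout) give about 80% power (beta 0.2) to detect a 1 h difference with SD 1.1 h at two-sided alpha 0.05.* The total of 50 is kept and the dropout step needs no change.

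If a one-sided test was intended, declare it in both sections and state about 88% power.

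If the sponsor wants 90% with a two-sided test, the number has to change instead: 26–27 evaluable per arm. That means 26/0.8 = 32.5 or 27/0.8 = 33.75, rounded up to 33 or 34 recruited per arm, or 66–68 in total.

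The restatement costs one paragraph, a few words in 5.9.2, and no extra patients. Its downside is that the stated power becomes less favourable. Only the last option adds recruitment, by 16–18 women.
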